### **C. Treatment assignment/randomization**

Participants will be randomized to receive one of three conditions: (1) the PP-based intervention, (2) an MI-based educational control condition, or (3) TAU. They will be randomized by a random-number generator and will be assigned a condition after Actigraph data is checked and has been found to be adequate at in-hospital Visit #2. The research assistant (RA)/blinded assessor who will conduct the follow-up assessments will be blind to the study condition. The interventionist and subjects will not be blind to the study condition.

## **V. STUDY PROCEDURES**

#### **A. Study visits/evaluations (See Table 1)**

**Initial visit (Week 1; in person).** The initial visit will occur in an MGH inpatient unit (for those recruited inpatient), in an office on the MGH main campus (for those recruited via opt-out letter), or over the phone (if a participant prefers to not come to the hospital for an in-person visit). Height and weight will be recorded (measured in person or taken from the medical record if inpatient). Participants then will meet with a member of the study staff (the study “trainer”) and complete self-report questionnaires. These questionnaires assess state optimism (State Optimism Measure; SOM), general optimism (Life Orientation Test-Revised; LOT-R), anxiety/depression (Hospital Anxiety and Depression Scale; HADS), positive emotions (Positive and Negative Affect Schedule; PANAS), HRQoL (Medical Outcomes Study; MOS, Short Form-12; SF-12), cardiac symptoms and heart failure-related QoL (Kansas City Cardiomyopathy Questionnaire; KCCQ), medication adherence (Self-Reported Medication Adherence [adapted from the Heart and Soul Study]; SRMA), and sodium intake (Scored Sodium Questionnaire; SSQ). Participants will also answer questions about their alcohol (using the AUDIT-C) and cigarette use. In sum, these scales should take approximately 30 minutes to complete.

After completing the baseline questionnaires, participants will receive an Actigraph GT3X+ accelerometer, and its use will be demonstrated by the trainer. We will measure activity at baseline (for 7 days) and in the 7 days following the 12 and 24-week assessments (we will send participants the ActiGraph in the mail at the appropriate time). In contrast to the pedometer, which is used by participants to monitor their activity, the ActiGraph accelerometer provides no information to participants about their physical activity and will only be used by the study team to measure physical activity as an outcome.

ActiGraph accelerometers are validated as measures of physical activity and have been used in numerous studies of physical activity in patients with medical illness. The accelerometer is a small 1.5” square device that can be worn on an elastic band (around the lower waist) or clipped onto a belt. It tracks the number of steps taken. After explaining how to use the accelerometer, the study trainer will schedule a time for the participant to come in for the second in person visit one week after the initial visit. In total this initial visit will take approximately 45 minutes.

#### **Second Visit (Week 2; in person).**

At the second in person visit, which will take place one week after the initial visit, we will collect the Actigraph from participants, and check to ensure participants had at least 5 valid days of data. At this point, participants will be randomized to one of the three conditions noted above. Patients in the TAU group will receive no further intervention and will be scheduled for a follow-up appointment in 12 weeks. Participants in the PP and goal-setting or MI-only conditions will be provided with a manual corresponding to their treatment condition, as well as a copy of *Learning to Live with Heart Failure*, a practical guide which is provided by MGH to all HF patients admitted to a cardiology unit at MGH.

**PP and goal-setting intervention:** The trainer then will introduce the participant to the PP and goal-setting portions of the intervention. For the PP portion, participants will be assigned the first exercise (Gratitude for Positive Events) and will be instructed to perform the exercise within the next week. Prior to completing the exercise, participants will be asked to rate their current level of happiness and optimism, using a 10-point Likert scale. Immediately after completing the

exercise, participants will rate the ease of exercise completion, overall utility of the exercise, and their current levels of happiness and optimism, all using 10-point Likert scales. For the first goal-setting session, the trainer will discuss the importance of physical activity in HF. Participants will be given a pedometer, which participants will use to monitor the number of steps they take daily over the following week. The trainer will instruct them in its use and set a goal for monitoring their baseline physical activity over the next week. This pedometer will not be used as an outcome measure but simply will be a tool that participants can use to monitor their activity.

*MI-based educational intervention:* Participants in the MI-only control group will similarly have the rationale of the MI-based health behavior program explained to them, and will be assigned the first exercise. They also will be given a pedometer for their personal use. We estimate that this portion of the visit will take approximately 20 minutes.

### **PP-based Health Behavior Intervention:**

Weekly phone sessions (Weeks 1-12). All participants will be asked to complete 12 weekly PP exercises and will be asked to speak with a study trainer weekly. In addition, in the final week, there will be a wrap-up phone call that focuses on the progress the participant has made in the program and makes a plan for continuing to use PP skills and engage in healthy activities in the future. Weekly phone sessions will last approximately 45 minutes. These calls will be recorded so that a percentage (10%) of these recordings can be reviewed to ensure that the PP and goal-setting portions of the intervention are being delivered as described in the protocol and trainer manual.

*Program Content.* All phone sessions will include (a) a review of the week's PP exercise (including the participant's ratings of pre- and post-exercise happiness, ease and helpfulness of the exercise, and optimism related to the future), (b) a discussion of the rationale of the next week's PP exercise through a guided review of the PP manual, and (c) assignment of the next week's PP exercise. Additionally, for the goal-setting portion, participants will (a) review their goals and behaviors from the prior week, (b) discuss techniques for improving health behavior adherence (e.g., monitoring physical activity, reading nutrition labels), and (c) set goals for the next week. The exercises and content for both PP and goal-setting portions of the program will be assigned in the same order for all participants receiving them. During the calls, the trainer and participant will also review the next section of the treatment manual and prepare for the upcoming week's exercise.

**Positive Psychology Exercises.** The PP exercises used in this study were selected based on their superior performance in our pre-pilot research and others' work. They will be grouped into four-week modules focusing on a different psychological state:

#### **Module 1: Gratitude-based activities**

##### **Session 1 (in-person visit): Gratitude for positive events.**

Participants recall three events, small or large, in the preceding week that were associated with satisfaction, happiness, pride, or other positive states.

##### **Session 2: Expressing gratitude.**

Participants write a letter of gratitude thanking a person for an act of kindness; participants may, at their discretion, share the letter with the other person.

**Session 3: Capitalizing on positive events.**

Participants identify three good events over the course of the week and then boost the positive feelings gained from them by sharing the events with others, or recording or celebrating the events in some way.

**Session 4: Integrating gratitude-based activities into daily life.**

Participants work to integrate one or more of the gratitude-based skills into their daily lives over the course of the week.

**Module 2: Strength-based activities**

**Session 5: Recalling a past success.**

Participants recall a prior event in which they experienced success. They write about the event, their contribution to the success, and the positive feelings evoked by recalling it. Finally, they consider how they might use the experience to be successful in the future.

**Session 6: Using personal strengths, part 1.**

Participants choose a personal strength that is important to them and then find a new way to use that strength over the following week.

**Session 7: Using personal strengths, part 2.**

Participants choose a second personal strength that is important to them and then find a new way to use that strength over the following week.

**Session 8: Integrating strength-based skills into daily life.**

Participants work to be more aware of successes that occur in their daily life and how they can use their strengths on an everyday basis.

**Module 3: Meaning-based activities**

**Session 9: Enjoyable and meaningful activities.**

Participants complete a series of self-selected activities that vary between those that bring immediate boosts in mood and those that are more deeply meaningful.

**Session 10: Performing acts of kindness.**

Participants complete three acts of kindness. The acts can be small or large, planned or spontaneous, but must be expressly completed to be kind to another. Participants then write how doing the acts made them feel.

**Session 11: The “Good Life”.**

Participants write about their ideal life over the next year in one or more life domains.

**Session 12: Integrating meaning-based activities into daily life.**

Participants work to perform enjoyable and meaningful acts for themselves and others in daily life.

### **Wrap-up session: Planning for the Future.**

Participants review the skills they have used in the program and make a plan for using these skills in everyday life moving forward.

**Goal-setting.** The goal-setting portion of the program aims to provide patients with knowledge about important HF-related health behaviors and assist them with setting goals to become more adherent to these health behaviors. This intervention will focus on three distinct health behaviors: physical activity, low-sodium diet, and medication adherence. These also will be divided into four-session modules, which will be completed in parallel to the PP exercises.

Each session follows the same structure. Study trainers will: (a) ask participants about their health goals, (b) provide education about a health behavior and/or refer them to their treatment team if clarification is needed, and (c) set a health behavior goal for the next week. Health behavior goals will be individualized to the participant, and participants will be encouraged to speak with their treatment team if they have any questions about appropriate goals for diet or physical activity. While all sessions will involve tracking participants' progress towards their health behavior goals, the educational components will vary from week to week:

### **Module 1: Increasing physical activity**

#### **Session 1 (in-person visit): Introduction to increasing physical activity.**

The trainer will review with participants the potential health benefits of physical activity, as well as participants' current physical activity. Participants will receive a pedometer and set a goal of monitoring their physical activity (through steps measured by the pedometer) over the next week.

#### **Session 2: Setting a SMART physical activity goal.**

Participants will learn about setting goals that are SMART (specific, measurable, attainable, relevant, and time-based) and will be encouraged to set a small behavioral goal related to physical activity.

#### **Session 3: Barriers and problem-solving related to physical activity.**

Participants will discuss ways to problem solve around barriers to physical activity.

#### **Session 4: Reviewing and reflecting on physical activity.**

Participants will reflect on their physical activity in the past few weeks and their progress to their overall physical activity goal. Based on their experience, they will revise their overall physical activity goal, if needed. Finally, participants will be mailed a graph of their weekly step counts to date.

### **Module 2: Maintaining gains related to physical activity**

#### **Session 5: Finding new routes.**

Participants will explore their neighborhood and brainstorm new places to walk

#### **Session 6: Using resources and making small changes.**

Participants will be asked to identify resources (community, friends/family, equipment) for engaging in physical activity and how they can use them to work toward their goals.

Participants also will think of ways to introduce small amounts of physical activity into their daily schedules.

**Session 7: Continuing progress and managing slips.**

Participants will learn about managing ‘slips’ or times when they get off track from their goals.

**Session 8: Reviewing and reflecting on physical activity.**

Participants will reflect on their physical activity in the past few weeks and their progress to their overall physical activity goal. Based on their experience, they will revise their overall physical activity goal, if needed. Finally, participants will be mailed a graph of their weekly step counts to date.

**Module 3: Other important healthy behaviors**

**Session 9: Introduction to a heart-healthy diet.**

The trainer will review with participants the potential health benefits of a low sodium diet, as well as participants’ current dietary habits. Participants will be encouraged to keep track of their salt intake over the next week and contact their physician if they are unsure how much sodium they should be consuming daily.

**Session 10: Setting a SMART heart-healthy diet goal.**

Participants will be encouraged to set a small behavioral goal related to diet and to continue to monitor their sodium intake.

**Session 11: Heart-healthy diet resources.**

Participants will be asked to identify resources (community, friends/family, low sodium diet recipes/books) for having a low sodium diet and how they can use them to work toward their goals. They will also discuss ways to problem solve around barriers to a heart-healthy diet.

**Session 12: Medication adherence and resources.**

The trainer will review with participants the importance of medication adherence, as well as participants’ current medication adherence. Trainers and participants will discuss different resources (e.g., medication pill boxes, electronic reminders) that can help participants remember to be adherent to their medications. They will also discuss ways to problem solve around barriers to medication adherence.

**Session 13: Planning for the future.**

Trainers will assist participants with reviewing their accomplishments and benefits gained from health behavior adherence thus far, and help them to create a plan for physical activity, heart-healthy diet, and medication adherence for the near future. Finally, participants will be mailed a graph of their weekly step counts to date.

At each session, health behavior goals will be reviewed with the participant, and if there are any concerns about the goals, participants will be encouraged to speak with their outpatient treatment team for clarification. Educational information will be based on the *Learning to Live with Heart*

Failure guide, which is provided to all patients with HF who are admitted to an MGH cardiology unit. Study staff will confer with the study cardiologist if any other questions arise.

Given the results of our prior PP studies, and given that this is a feasibility study (i.e., we want to assess participants' willingness to complete the exercises), we will expect participants to complete at least 7 PP exercises / goal-setting sessions. In other words, if a participant completes at least 7 sessions, missed sessions will not be considered a deviation from the protocol.

**MI-based educational control condition:**

The MI-based educational intervention was selected as the active control condition for several reasons. The inclusion of MI and education regarding key cardiac health behaviors aims to increase the retention of participants included in this condition. However, the focus of this intervention on multiple health behaviors and the lack of specific goal-setting make it less likely that this control intervention will significantly impact physical activity (our primary health behavior outcome) and our other health behaviors of interest. Finally, as an attentional control, it has a parallel structure to the experimental arm with a treatment manual, weekly exercises, and weekly calls to review exercises.

Each week, participants will learn about a different health behavior topic related to cardiac health. They will also be introduced to motivational interviewing topics in concert with the health behavior education topics. The intervention is divided into five sections, focusing on five different important cardiac health-related topics:

**Part One: A Healthy Heart**

**Understanding Heart Disease and Its Risks (Session 1)**

Participants will review information about heart disease, including HF, as well as information about heart disease and its associated risk factors.

**How to Take Care of Your Heart (Session 2)**

Participants will review information about the importance of health behaviors to reduce the risk of heart disease.

**Part Two: Staying Active**

**The Importance of Staying Active (Session 3)**

Participants will review the cardiovascular benefits of physical activity, questions to ask their physician prior to starting physical activity, and ways to set goals related to physical activity.

**How You Can Stay Active (Session 4)**

Participants will identify one way in which they wish to change their physical activity. They will discuss the importance of making the change and their confidence about being able to do so. Finally, they will create a list of pros and cons for behavior change.

**Barriers to and Resources for Activity (Session 5)**

Participants will identify barriers to physical activity in their life and brainstorm ways to problem-solve around those barriers. Furthermore, they will identify social, community-based, and equipment resources available to help them with physical activity.

### Part Three: Heart-healthy Diet

#### **Benefits of a Heart-Healthy Diet** (*Session 6*)

Participants will learn about the cardiovascular benefits of a heart-healthy diet. They will be encouraged to track their food intake over the next week to learn more about their diet.

#### **Reducing Sodium** (*Session 7*)

Participants will learn about the importance of reducing sodium in their diet. Next, they will identify one way in which they wish to change their diet. They will discuss the importance of making the change and their confidence about being able to do so. Finally, they will create a list of pros and cons for behavior change.

#### **Barriers to and Resources for a Heart-healthy Diet** (*Session 8*)

Participants will review how to properly read a food label and learn techniques to make healthy decisions while food shopping. They also will identify barriers to a healthy diet, problem-solve those barriers, and identify resources that can help to improve their diet.

### Part Four: Taking Medications

#### **Taking Medications Regularly** (*Session 9*)

Participants will review the importance of medication adherence and learn about medications typically prescribed for HF. Participants will be encouraged to create a list of their current medications, as well as any questions they have for their physicians about their medications.

#### **Barriers to and Resources for Taking Medications Regularly** (*Session 10*)

Participants will identify barriers to taking medications, problem-solve those barriers, and identify resources to help them maintain adherence to medications.

### Part Five: Stress Reduction

#### **How Relaxation Can Help Your Heart** (*Session 11*)

Participants will learn about the risks of acute and chronic stress. They will learn to recognize their reactions to stress and will be introduced to methods for relieving stress.

#### **How to Practice Relaxation Regularly** (*Session 12*)

Participants will learn about relaxation response exercises and ways to incorporate these exercises into daily life.

#### **Planning for the Future** (*Session 13*)

Participants will review the information learned over the course of the program and think of ways to remain healthy after the end of the program.

### **Treatment as Usual (TAU):**

Participants in the TAU group will not receive any interventions between the baseline visit and follow-up visits. The inclusion of this group will allow us to examine the overall impact of the PP-based intervention compared to TAU, as well as its impact compared to an active comparator.

### Follow Ups:

**Follow-up phone calls (Week 12 and Week 24 [post randomization]).** At Weeks 12 and 24, a member of the study staff will call participants to repeat the self-report questionnaires that were administered at baseline. These questionnaires assess state optimism (State Optimism Measure; SOM), general optimism (LOT-R), positive affect (PANAS), overall health behavior adherence (MOS), anxiety/depression (HADS), HRQoL (SF-12), cardiac symptoms and HF-related QoL (KCCQ), medication adherence (SRMA), and sodium intake (SSQ). Participants will also be asked about cardiac-related hospital readmissions and cardiac rehabilitation, and to rate their overall satisfaction with the treatment they received for their cardiac condition over the course of the study on a scale of 0 (not at all satisfied) to 10 (completely satisfied). Finally, patients will be asked about their experience in the study, including any aspects of the intervention or study procedures that could be improved, during follow-up assessment. In sum, these scales should take approximately 30-40 minutes to complete. If participants would rather complete the follow-up questionnaires in written form rather than over the phone, we will send them a paper packet at the time of the follow-up.

**Training.** [name] (PI) has substantial experience in explaining and delivering PP exercises from their studies in cardiac and psychiatric patients. The PP exercises for this trial have been identified via published literature, or directly from researchers, and modified appropriately for this population. Additional text outlining the rationale and instructions for each exercise are located in the written packets for each exercise that are provided to participants. [name] will engage in several training exercises prior to study initiation. He will review the treatment manual and our team's prior training manuals related to these exercises. He will then complete all exercises to gain experience performing and reviewing each exercise.

[name] also has significant experience with providing guidance and motivation towards goal-setting from the ongoing work in cardiac patients. [name] currently is the Project Director of another study examining the efficacy of PP and goal-setting interventions in patients with ACS. This study utilizes a nearly identical MI-based control condition, with which [name] has experience. Both the goal-setting portion of the PP-based intervention and MI-based control condition aim to improve health behaviors that studies have shown to be critical for cardiac health in patients with HF. Similar to his training related to the PP exercises, [name] will review the treatment manuals for this project and complete each exercise to gain experience providing education and setting goals related to physical activity, sodium restriction, and medication adherence.

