#### Measures:

- Optimism: LOT-R; SOM
- Positive affect: PANAS (primary outcome measure for this aim)
- Anxiety/depression: HADS

We will examine between-group differences (PP-based condition vs. MI-informed educational control and PP-based condition vs. TAU) on changes in each of these psychological outcomes to assess the impact of the intervention compared to both an active control and TAU. The primary study endpoint will be 12 weeks, though we will secondarily assess the impact of the intervention on outcomes at 24 weeks as well.

**Aim #3 (Impact on functional outcomes and health behaviors):** To examine the impact of the intervention on physical activity (steps, as measured by accelerometer; primary health behavior outcome), medication adherence, sodium intake, HF-related QoL, and generic HRQoL, compared to treatment as usual and an MI-based health behavior education intervention.

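### An open question about the intervention in the week-12 follow-up call can reveal the arm to the blinded assessor before the secondary week-24 phone-administered scales

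*Combined protocol and SAP*

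**What the plan says.** Section IV.C (Treatment assignment/randomization) sets out the blinding: "The research assistant (RA)/blinded assessor who will conduct the follow-up assessments will be blind to the study condition". The next sentence adds: "The interventionist and subjects will not be blind to the study condition".

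The Follow Ups part of section V.A describes both calls in one paragraph: "At Weeks 12 and 24, a member of the study staff will call participants to repeat the self-report questionnaires that were administered at baseline". In the same call participants also "rate their overall satisfaction with the treatment they received for their cardiac condition over the course of the study". The paragraph then ends its list of content with the open question: "patients will be asked about their experience in the study, including any aspects of the intervention or study procedures that could be improved". A participant who prefers paper may be sent the questionnaires instead.

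According to the Initial visit text in section V.A, the accelerometer is worn "in the 7 days following the 12 and 24-week assessments". On time points, section VI.A and B states under Aim 2: "The primary study endpoint will be 12 weeks, though we will secondarily assess the impact of the intervention on outcomes at 24 weeks as well".

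**The concern.** Participants know their arm, and the last item of the week-12 call invites them to talk about it. Someone who mentions gratitude letters or personal strengths is in the positive psychology (PP) arm. Someone who mentions relaxation sessions or lists of pros and cons is in the motivational interviewing (MI) arm. A treatment-as-usual (TAU) participant has no intervention to comment on: "Participants in the TAU group will not receive any interventions between the baseline visit and follow-up visits".

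An assessor who has heard such an answer may know the arm when phoning the same participant again at week 24. Scales read aloud by an interviewer are open to tone, prompting and the handling of unclear replies. Blinding of the follow-up assessor is the only blinding the plan describes. At stake are the week-24 PP versus MI and PP versus TAU contrasts on the phone-administered scales, and any later statement that those outcomes were collected blind.

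**Working it through.** **Order of events.** Putting sections IV.C, V.A and V.E together gives this sequence:

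1. Week-12 scales by phone, including PANAS (primary psychological outcome) and KCCQ (primary functional outcome).
2. The open experience question, placed last in the call.
3. Week-12 accelerometer wear, in the seven days after the call.
4. Week-24 scales by phone.
5. The open experience question again.
6. Week-24 accelerometer wear.

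Step 2 follows step 1, so the week-12 questionnaire data are already in hand. Step 2 precedes step 4, so the week-24 scales are exposed.

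**Safeguards looked for.** The documents do not give the question to another person, hold it back until week 24, plan a different caller at week 24, ask participants not to disclose their arm, or have the assessor record unblinding. Section IV.C and the Confidentiality text in section VII.D both refer to a single research assistant for follow-up assessments. The paper option depends on participant preference and is not a blinding measure.

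**Number exposed.** The question is put to patients generally, so all three arms are asked. With 20 per group (section VI.D), that is 3 × 20 = 60 before attrition.

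**Illustration of size.** The plan gives no figure for interviewer influence, so there is nothing of its own to reproduce. The inputs are:

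- n = 20 per arm (section VI.D), with no loss by week 24 (assumption).
- Two-sided test at 0.05 (section VI.C), treated as a z test.
- No true effect, and a differential shift b of 0.1, 0.2 or 0.3 SD on the contrast (assumption).
- SE without baseline adjustment: √(2/20) = 0.316 SD.
- SE with baseline adjustment at a baseline to follow-up correlation of 0.6 (assumption): 0.316 × √(1 − 0.6²) = 0.316 × 0.8 = 0.253 SD.

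Rejection probability = P(Z > 1.96 − b/SE) + P(Z < −1.96 − b/SE).

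| b (SD) | SE = 0.316 | SE = 0.253 |
|---|---|---|
| 0.1 | 0.0501 + 0.0114 = 6.2% | 0.0588 + 0.0093 = 6.8% |
| 0.2 | 0.0922 + 0.0048 = 9.7% | 0.1211 + 0.0030 = 12.4% |
| 0.3 | 0.1559 + 0.0018 = 15.8% | 0.2194 + 0.0008 = 22.0% |

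A simple change-score analysis at the same correlation has SE = 0.316 × √(2 × 0.4) = 0.283 SD and falls between the two columns.

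**The case against.** The case for leaving this alone has several parts.

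- **Week 12 is the main time point and week 24 is secondary.** This stands. The week-12 PANAS, KCCQ and other scales are complete before the question is put, and feasibility is a count of sessions completed.
- **The trial is a pilot.** Section VI.D says it is not designed to detect between-group differences in health behavior outcomes at either follow-up, and the Aim 2 and 3 hypotheses on control comparisons ask only for numerically larger gains. This limits the consequence. Section VI.C still plans two-tailed tests at 0.05 at both time points, and a numerical comparison is no less open to a shift than a test.
- **The wording leaves room.** The sentence does not name a week, Table 1 has no row for the question, and the caller is described only as a staff member. A different week-24 caller is possible. However, the paragraph is headed for both weeks, and nothing restricts the question to week 24 or plans a second caller.
- **Self-report from unblinded participants carries bias anyway.** This is true, and the satisfaction rating could also prompt disclosure. Neither point is a reason to add an avoidable route.

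Two stronger readings are tempting. A reader might infer that the primary health behavior outcome, steps, is compromised because wear follows the call. The documents do not support that: steps are recorded by a device that shows participants nothing, and the validity rules are fixed (480 minutes for a valid day, five valid days, re-wear until met, section V.E). The assessor's knowledge could act only through staff contact about wear or re-wear. A reader might also infer that the procedure abolishes blinding. The text shows only that it can reveal the arm. Not every answer will, and some participants may use paper.

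**Conclusion.** The point holds in a limited form and should be acted on. As written, the week-12 call can unblind the declared blind assessor before the secondary week-24 phone-administered scales. The week-12 self-report scores and the primary feasibility outcome are not affected, and any effect on steps is minor.

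The size of any bias is unknown. The range of about 6% to 22% is a sensitivity illustration. It rests on an assumed shift of 0.1 to 0.3 SD, full retention of 20 per arm and, at the upper end, an assumed correlation of 0.6. It should not be read as an estimate of what will happen. The conclusion itself rests on reading the question as asked at both weeks and on the same person calling at both. The documents point to both readings but do not state either outright.

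**What to change.** Take the experience question out of the blinded assessor's week-12 call. Collect it at week 12 in one of two ways:

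- through existing unblinded staff, such as the study trainer, in a brief separate contact after the scales are done; or
- on a short self-completed form that only unblinded staff open. It could travel in the pre-paid accelerometer return envelope (section VII.C), provided someone other than the blinded assessor opens the envelope.

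At week 24, ask the question only after all outcome scales are complete. The week-24 accelerometer week would still follow, but for the reason given above the exposure there is small. Have the assessor record at each call whether the arm was disclosed, including through remarks on the satisfaction item, so that blinding at week 24 can be reported as it actually was. Add the question to Table 1 with its week and the role that asks it.

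The cost is a script change and either one short form or one brief contact, with no added outcome, visit or post. Written feedback may be briefer, or the feedback must be gathered separately. That matters a little because section VIII.C uses participant dissatisfaction to decide whether to alter the protocol, so the week-12 feedback should be moved and not dropped.
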